### **3.2.3. Complete Response (CR) Rate**

CR rate is defined as the proportion of subjects achieving the best response rating of CR based on the Lugano Classification, as determined by IRRC or Investigator.

The primary analysis for CR will include CR prior to first PD.

As a supportive analysis, CR will be summarized by including CR achieved overall. i.e, throughout the duration of the study for subjects in IS group switching to CS group.

### **3.2.4. Progression-Free Survival (PFS)**

PFS is defined as time from first dose of study drug until first disease progression or death from any cause for all groups. Disease progression criteria are defined per Modified Lugano Response Criteria and will be assessed by IRRC and Investigator, independently.

As supportive analysis, PFS2 will be defined as time from first dose of CS after switching until disease progression or death from any cause, and PFS3 will be defined as time from first dose of study drug until disease progression or death from any cause after switching back to the CS. PFS2 and PFS3 are only defined for patients in the ITT IS Population ([Section 4.2](#)) who switched back to the CS.

The censoring rule for PFS will be the same as the ones for primary analysis for DOR ([Table 3](#)), with the exception that subjects with Incomplete or no baseline tumor assessments or no additional follow-up data obtained will be censored at first dose date.

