## 2.3. Brief Description

Under Protocol Amendment 2, this is a global, multicenter, open label, single-arm, phase 2 study of the PI3K $\delta$  inhibitor ME-401 (zandelisib) in subjects with relapsed/refractory FL or MZL. ME-401 will be administered orally at a dose of 60 mg given once a day in 28-day cycles, with the first day of treatment designated as Day 1. Treatment with ME-401 can be administered based on a continuous schedule (CS) or an intermittent schedule (IS).

[figure not shown]
The CS (or Group A in Protocol Amendment 1) includes daily dosing for the whole duration of a treatment cycle until protocol-defined criteria is met for treatment interruption, modification to intermittent dosing to manage toxicity, or discontinuation.

The IS (or Group B in Protocol Amendment 1) includes:

- continuous daily therapy for the initial 2 cycles (~56 days) of treatment
- the intermittent treatment begins at Cycle 3, with ME-401 administered daily for the first 7 days of every 28-day cycle (7 days on treatment and 21 days off treatment)

Under Protocol Amendment 1 (Figure 1a), subjects were randomized 1:1 to receive CS or IS. Since Protocol Amendment 2 (Figure 1b), the initial CS treatment arm was terminated, and all new subjects were enrolled to receive therapy on the IS only. If CS subjects already completed 2 initial cycles of therapy, they were switched to IS dosing after they complete therapy in the ongoing cycle of treatment, and if they had not completed the first 2 cycles of therapy they were switched to IS dosing after completion of the first two cycles of therapy on CS. Subjects who progress on IS dosing may be switched to CS dosing. Subjects will continue to receive study drug in accordance with the IS dosing regimen (or CS dosing regimen if switched from IS after disease progression [PD]) until investigator-assessed disease progression or unmanageable toxicity requiring treatment discontinuation, subject's decision to withdraw their consent to participate on study, or study closure by the Sponsor.

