## 2.5. Treatment Assignment

Under Protocol Amendment 1 (Figure 1a), subjects are randomized 1:1 to Group A (CS) or Group B (IS), stratified accordingly to tumor bulk (largest lymphoid mass  $< 5$  cm vs.  $\geq 5$ cm) and disease response to last therapy (relapse vs. refractory).

Since Protocol Amendment 2 (Figure 1b), this is an open-label and single-arm phase 2 study that all new subjects will be enrolled and treated by IS dosing only. During the first 2 cycles, subjects will receive open-label ME-401 administered at 60 mg once daily. After completing 2 cycles of daily therapy, subjects will continue ME-401 administered at 60 mg daily for the first 7 days of every 28-day cycle (7 days on treatment and 21 days off treatment). Subjects who progress disease on IS dosing have the option to have their ME-401 dosing switched to CS dosing.

Since Protocol Amendment 2, the initial CS treatment arm was terminated, and switched to IS dosing. For CS Subjects from Protocol Amendment 1, those who already completed 2 initial cycles of therapy were switched to IS dosing once they complete the ongoing cycle; those who had not completed the first 2 cycles were switched to IS dosing after the first 2 cycles.

For subjects who experience toxicity during the first 2 cycles while receiving daily therapy with ME-401, dose interruption followed by a switch to the intermittent schedule daily dosing for the first 7 days of every 28-day cycle is allowed. Subjects who experience toxicities on the IS will be managed by the instructions for management of potential drug-related toxicity (Protocol Amendment 3, [Table 4](#)), which may include dose interruption or permanent discontinuation of ME-401.

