**Table 2: Censoring Rules for the Primary Analysis of DOR and DORR**

Situation	Date of Event or Censoring	Outcome
Progression documented	Date of earliest assessment which revealed progression determined by the IRRC	Event
Death before first PD assessment	Date of death	Event
Death between adequate assessment visits	Date of death	Event
No progression, nor death	Date of last adequate assessment with evidence of no progression by the IRRC	Censored
Discontinuation for any reason other than documented PD or death	Date of last adequate assessment with evidence of no progression by the IRRC	Censored
Loss to follow-up	Date of last adequate assessment with evidence of no progression by the IRRC	Censored
Switching back to CS dosing schedule without evidence of PD by IRRC prior to switching	Date of last adequate assessment with evidence of no progression by the IRRC before switching back to the CS dosing schedule	Censored
New anti-lymphoma treatment started without evidence of PD by IRRC	Date of last adequate assessment with evidence of no progression by the IRRC before the start of new anti-lymphoma treatment	Censored
Death or progression after two or more consecutive missed scheduled visits	Date of last adequate assessment with evidence of no progression by the IRRC	Censored

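### The supportive endpoint PFS3 starts at first dose but admits only subjects who later switched to continuous dosing, so its curve cannot be read against PFS or as the result of intermittent-then-continuous dosing

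*SAP*

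**What the plan says.** SAP 3.2.4 sets out three time-to-event measures.

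- Main PFS: "PFS is defined as time from first dose of study drug until first disease progression or death from any cause for all groups".
- PFS2: "As supportive analysis, PFS2 will be defined as time from first dose of CS after switching". Its clock and its population both begin at the switch.
- PFS3: "PFS3 will be defined as time from first dose of study drug until disease progression or death from any cause after switching back" to CS. Its clock begins at first dose, but only events after the switch count.

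On population, the section says "PFS2 and PFS3 are only defined for patients in the ITT IS Population" "who switched back to the CS". Both measures are labelled supportive.

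The switch is optional and normally follows progression. SAP 2.3 says "Subjects who progress on IS dosing may be switched to CS dosing", and SAP 2.5 says "Subjects who progress disease on IS dosing have the option to have their ME-401 dosing switched to CS dosing". Table 2 also foresees another route: "Switching back to CS dosing schedule without evidence of PD by IRRC prior to switching".

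No landmark, delayed entry or time-dependent handling is given for PFS3. SAP 7.2.4 and Table 4 of the SAP name neither PFS2 nor PFS3. The protocol (7.2.3, 11.2.2) does not define them.

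**The concern.** A time-to-event curve is interpretable when everyone in it is identifiable, and at risk, at time zero. PFS3 fails both conditions. A subject qualifies only after remaining alive to the switch and choosing it, usually after progressing, and before that moment no PFS3 event is possible.

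Two distortions follow, and they act in opposite directions. The guaranteed event-free time lifts the early curve. Leaving out subjects still progression-free on IS at the data cutoff removes the best outcomes and lowers the later curve.

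A curve labelled PFS3 and measured from first dose invites comparison with PFS, and invites reading as total disease control on IS followed by CS. It supports neither use, and because the net bias has no fixed sign, a footnote cannot correct it.

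**Working it through.** The plan states no figure for PFS3, so there is nothing to reproduce. The check is logical first and then numerical.

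**1. Earliest possible event.** Protocol Appendix 1 puts the first response scan at day 61 (±7), and Protocol 7.1 restarts the scan calendar at the date of progression. With progression found at scheduled scans, the earliest PFS3 progression is about day 61 + 61 = 122, or 54 + 54 = 108 with both windows at their early limit. Only a death or an unscheduled scan after the switch could come sooner.

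**2. Within one subject.** The first progression after the switch cannot precede the first progression overall, so PFS3 ≥ PFS for every individual. A simulated check found no exceptions.

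**3. Group curves.** These inputs are assumed, because the documents do not give them:
- median time to progression on IS, m1 = 8, 12 or 18 months
- median time from switch to next event, m2 = 3, 6 or 9 months
- share of progressors who switch, s = 30%, 60% or 100%
- exponential times, with cutoff uniform over 14 to 30 months from first dose (the lower bound is the follow-up of about 14 months in the protocol synopsis)

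With λ = ln 2 / m:
- PFS: S1(t) = exp(−λ1·t)
- If everyone switched: S12(t) = [λ2·exp(−λ1·t) − λ1·exp(−λ2·t)] / (λ2 − λ1)
- Share progressing before cutoff: p = 1 − [exp(−14λ1) − exp(−30λ1)] / (16λ1)
- PFS3 as written, for t ≤ 14 months: 1 − [1 − S12(t)] / p
- All-subject version: s·S12(t) + (1 − s)·S1(t)

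Worked case, m1 = 18, m2 = 3, t = 12: S1 = 0.630, S12 = 0.7435 and p = 0.5646. PFS3 = 1 − 0.2565/0.5646 = 0.546. The all-subject version at s = 60% is 0.6 × 0.7435 + 0.4 × 0.630 = 0.698.

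| m1 / m2 | t (months) | PFS | PFS3 as written | All-subject (s) |
|---|---|---|---|---|
| 18 / 3 | 6 | 0.79 | 0.83 | 0.86 (60%) |
| 18 / 3 | 12 | 0.63 | 0.55 | 0.70 (60%) |
| 8 / 9 | 6 | 0.59 | 0.90 | 0.69 (30%) |
| 8 / 9 | 12 | 0.35 | 0.69 | 0.47 (30%) |

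In the 18/3 case PFS3 starts above PFS and crosses below it. The formula shows why. If p were 1, PFS3 would equal S12 and always exceed PFS; as p falls, late progressors drop out and the curve sinks. The switching share s does not appear in PFS3 at all.

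**4. Full range.** Kaplan-Meier on 400,000 simulated subjects in each of the 27 combinations:
- At 3 months PFS3 is 0.92–0.98 against PFS 0.77–0.89. At 6 months it is 0.76–0.93 against about 0.59–0.79.
- Median PFS3 is below median PFS at 18/3 (13.0 vs 18) and 18/6 (16.7 vs 18), equal at 12/3 (12.0 each), and longer in the other six pairs, for example 17.7 vs 8 at 8/9.
- At 8/3, median PFS3 stays at 10.7–10.8 months for s = 30%, 60% and 100%, while the all-subject median moves from 9.4 to 10.9 to 12.7.
- Against the all-subject median, PFS3 can be higher (17.7 vs 11.0 at 8/9/30%) or lower (12.9 vs 22.6 at 18/3/100%).

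**5. On the protocol's scan calendar** (60% switching, 10% of events deaths, cutoff 14 to 32 months). With IS median 18 and no CS activity, median PFS3 is 11 months, against about 18–19 for PFS and 20 for the all-subject version. With IS median 9 and CS median 4, 6-month PFS3 is 86%, against 63% for PFS and 77% for the all-subject version.

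**The case against.** The strongest reply is that the SAP never claims what is being criticised. It calls PFS3 supportive, says openly that it covers switchers only, plans no comparison with PFS, and specifies no Kaplan-Meier output for it. That stands, and it limits the weight of the point.

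Several stronger readings are tempting and should be set aside.

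- **That PFS3 is the trial's estimate of the IS-then-CS strategy, or its only measure across the switch.** The SAP states no such estimand. TTF (SAP 3.2.5, 7.2.5) runs from first dose in the PEP FL and ITT MZL populations. Under Protocol 5.7 a subject who moves to CS at progression has not stopped treatment, so the switch is not a TTF event on its wording. OS also spans the switch. What remains is that TTF measures time on treatment and OS measures death, so neither replaces a progression-based measure.
- **That PFS3 can be shorter than PFS for a subject.** It cannot (step 2). Only the switchers' curve can fall below the curve for all subjects.
- **That PFS3 varies with the switching rate.** It does not under these assumptions. The all-subject alternative does.
- **That an all-subject redefinition removes every difficulty.** A first progression would count as an event or be set aside according to a later, optional choice, and the gap between progression and switch would stay event-free for switchers. This is a real cost of that option.

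**Conclusion.** The concern holds for PFS3 as defined. Selection on a post-baseline event, combined with a clock started at first dose, follows from the wording alone and needs no assumption. No other part of the SAP corrects it.

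The size and direction do rest on assumptions: exponential times, the chosen medians and switching shares, and the cutoff distribution. Within those ranges the switchers' median runs from 5 months below the PFS median (13.0 vs 18) to 9.7 months above it (17.7 vs 8). These figures show what is possible and do not predict the trial's result.

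Severity is minor. No hypothesis or decision uses PFS3, and a reader should not infer any effect on ORR, DOR or the main PFS analysis. PFS2 does not share the flaw, because its clock starts where its population is defined.

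**What to change.** Choose one of two edits to SAP 3.2.4.

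**(a) Delete PFS3.** Keep PFS2, from the first CS dose, as the descriptive measure in switchers. This is the simpler course.

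**(b) Redefine PFS3** in all subjects of the PEP FL, ITT IS FL and ITT MZL populations, from first dose. For subjects who switched to CS, the event is progression after the switch or death. For all others, it is first progression or death. Then also:
- state how switches without IRRC-documented progression are handled. Tables 2 and 3 treat them differently, and 3.2.4 invokes the primary DOR rules while citing Table 3, which is the supportive set
- report the number who switched
- label the endpoint supportive

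Under either option, correct the population name: SAP 4.2 defines an ITT IS FL population, not the one named in 3.2.4, so the place of MZL switchers is unclear.

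Cost: a few sentences and, for (b), one derived variable, with no new data. The downside of (b) is that non-switchers contribute their first progression, so the estimate depends on the share of progressors who switch. A SAP revision is due in any case, since SAP 2.4 still plans 64 MZL subjects while Protocol 11.1 records closure at 32.

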### **3.2.5. Time to Treatment Failure (TTF)**

Time to treatment failure is defined as time from the first dose of study drug to treatment failure. Treatment failure is defined as any treatment discontinuation due to PD, toxicity, or death.

Censoring rule for TTF:

- Subjects who are still alive and on treatment will be censored at the last disease assessment date indicating the absence of progression;
- Subjects who have treatment discontinued for reasons other than PD, AE, or death, will be censored at the treatment discontinuation date.

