### 3. STUDY OBJECTIVES

This is a single-arm study. The objectives of this study are to evaluate the efficacy and safety of the IS dosing regimen of ME-401.

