### **5.7. Discontinuation of ME-401 Treatment**

Administration of ME-401 will continue unless one of the following occurs:

- Progressive disease, unless the Investigator deems a switch to continuous dosing is in the best interest of the subject and the subject agrees to continue treatment with CS dosing
- Unacceptable AE(s) considered related/possibly related to ME-401 despite appropriate therapy and modified dosing schedule
- Withdrawal of consent by the subject
- Changes in the subject's medical condition that render further administration of ME-401 unacceptable in the judgement of the Principal Investigator or Sponsor
- Non-compliance
- Termination of study by Sponsor

Subjects who discontinue from therapy should be followed for efficacy and survival unless they withdraw consent to participate.

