### **7.2.4. Time to Treatment Failure (TTF)**

Time to treatment failure will be assessed as a secondary endpoint and is defined as the time from first dose of study drug to treatment failure.

Treatment failure is defined as any treatment discontinuation due to disease progression, toxicity, or death.

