### **7.2.5. Time to Treatment Failure (TTF)**

TTF is the time from the first dose of study drug to treatment failure (any treatment discontinuation due to PD, toxicity, or death). The analysis of TTF will be performed based on the assessment by IRRC and investigator, separately.

TTF will be summarized using Kaplan-Meier summary statistics for PEP FL and ITT MZL population. The median TTF with 95% CIs (Brookmeyer and Crowley method), number of events, number censored, and KM plot of proportion of subjects without treatment failure over time will be presented. TTF will be reported in months. Estimate and 95% CI for 1-year TTF rate, and reverse KM estimate median with 95% CI for follow-up time (months) will be summarized.

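### TTF does not count progression on the intermittent schedule when the subject switches to continuous dosing, which biases the 1-year TTF rate for the intermittent regimen upward

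*SAP*

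**What the plan says.** Protocol 7.2.4 sets the event: "Treatment failure is defined as any treatment discontinuation due to disease progression, toxicity, or death". SAP 3.2.5 repeats it: "Treatment failure is defined as any treatment discontinuation due to PD, toxicity, or death". Both measure from the first dose of study drug.

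Progression need not end treatment. SAP 2.3 states: "Subjects who progress on IS dosing may be switched to CS dosing". Protocol 5.7 writes the exception into its list of reasons for stopping ME-401: "Progressive disease, unless the Investigator deems a switch to continuous dosing is in the best interest of the subject".

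For subjects without an event who remain on drug, SAP 3.2.5 says: "Subjects who are still alive and on treatment will be censored at the last disease assessment date indicating the absence of progression". Subjects who stop for other reasons are censored at the discontinuation date. Neither TTF section has a rule for subjects who have progressed and switched.

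SAP 7.2.5 summarises TTF by Kaplan-Meier in the FL primary efficacy population and the ITT MZL population, with a median and "Estimate and 95% CI for 1-year TTF rate", separately by IRRC and investigator assessment.

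Protocol 3 names the target: "The objectives of this study are to evaluate the efficacy and safety of the IS dosing regimen of ME-401".

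**The concern.** A subject whose lymphoma progresses on the IS has failed the IS. Under the TTF definition that failure is postponed to a later stop of CS, or removed by censoring if CS is still running at the cutoff. Only subjects who progressed on the IS are treated this way, so the more of them switch, the better the IS looks at one year.

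The other main endpoints do not work like this. The primary ORR and CR-rate analyses use response before first progression, DOR ends at first progression or death, and for PFS SAP 3.2.4 says: "PFS is defined as time from first dose of study drug until first disease progression or death from any cause for all groups". Time after the switch has its own endpoints (PFS2, PFS3, recapture of response, DORR), and the DOR censoring rules in SAP Table 2 have a row for switching. Protocol 7.2.6 states that OS is taken regardless of dosing schedule. TTF has neither a switch rule nor such a statement, which looks more like an omission than a choice.

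**Working it through.** **No plan figure to reproduce.** The documents give no assumed or expected TTF median, rate or event count.

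**What happens to one subject.** Take progression found at the day-274 scan of Protocol Appendix 1, followed by a switch to CS.
- First progression as failure: event at 274/30.4375 = 9.0 months.
- SAP rule, CS stopped for progression on day 365: event at 365/30.4375 = 12.0 months.
- SAP rule, still on CS at cutoff, literal reading: censored at the day-182 scan, 182/30.4375 = 6.0 months. The progression itself causes this censoring, so it is informative.
- SAP rule, still on CS at cutoff, progression judged against the new baseline (Protocol 7.1, SAP 3.2.6): censored at a scan after day 274.

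**Inputs for the size.**
- From the documents: scan days 61, 121, 182, 274, 365, 456, 547, 730 and onward.
- Assumed, because not given: median time to progression 9 or 12 months; 25, 50 or 75% of progressors switch; median time on CS 3, 6 or 9 months; toxicity stops 1% per month; other stops 0.5% per month; follow-up 6–14 or 14–24 months. This makes 2 × 3 × 3 × 2 = 36 scenarios.
- The only anchor for time to progression is the Phase 1b IS median DOR of 11.2 months (Protocol 1.6.2.4). A later cut in Protocol 2.3 reports that median as not reached.

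**Hand check of the central case** (progression median 12 months, 50% switch, CS median 6 months, scans rounded to months 2, 4, 6, 9, 12).

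With first progression as failure, the 1-year rate is 0.5^(12/12) × exp(−0.01 × 12) = 0.5 × 0.8869 = 0.4435.

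If switchers count only when CS stops, add for each scan month t: P(progression found at t) × P(no toxicity stop by t) × switch share × 0.5^((12 − t)/6).

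| t | P(progression at t) | P(no toxicity stop) | Product | CS running at month 12 | Contribution |
|---|---|---|---|---|---|
| 2 | 0.1091 | 0.9802 | 0.1069 | 0.3150 | 0.0337 |
| 4 | 0.0972 | 0.9608 | 0.0934 | 0.3969 | 0.0371 |
| 6 | 0.0866 | 0.9418 | 0.0816 | 0.5000 | 0.0408 |
| 9 | 0.1125 | 0.9139 | 0.1028 | 0.7071 | 0.0727 |
| 12 | 0.0946 | 0.8869 | 0.0839 | 1.0000 | 0.0839 |

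The contributions sum to 0.268. With half switching, 0.4435 + 0.5 × 0.268 = 0.5775.

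**Simulation** (200,000 subjects per scenario, Kaplan-Meier). Central case with 14–24 months of follow-up:

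| Rule | 1-year rate | Median (months) |
|---|---|---|
| First progression on IS is failure | 44.5% | 12.0 |
| SAP rule, literal (censor before progression) | 56.0% | 14.7 |
| SAP rule, censor after switch | 57.8% | 15.0 |

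The hand values of 44.35% and 57.75% agree with the first and third rows.

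Over all 36 scenarios:
- Literal reading: the 1-year rate rose in every one, by about 1 to 12 points with 6–14 months of follow-up and 4 to 23 points with 14–24 months.
- Censoring after the switch: it rose by about 3 to 28 points.
- Median, literal reading: mostly higher or unchanged (at most 9.0 to 14.2 months). In two short-follow-up scenarios it was slightly lower (11.3 and 11.5 against 12.0), because the curve steps at scan dates.
- Between 14% and 69% of switchers were still on CS at cutoff and so censored.

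**The case against.** The best defence is that TTF means failure of ME-401 on any schedule. It runs from first dose of study drug, it is listed under the efficacy of ME-401, and study drug includes CS after progression. That estimand is coherent, but the text does not deliver it. A subject doing well on CS would be failure-free up to the cutoff, yet the literal rule censors that subject before the progression. Protocol 3 also names the IS regimen as the target.

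It can also be said that the drafter had only non-progressors in mind in the censoring rule, and that the IRRC/investigator split in SAP 7.2.5 makes little sense if discontinuation alone counts, so assessed progression may have been meant to matter. Both are plausible. They support calling the censoring date for switchers ambiguous, which it is, but neither ambiguous date removes the bias.

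The contrast with PFS is less tidy than its definition suggests. SAP 3.2.4 says PFS follows the primary DOR censoring rules but points to Table 3, the supportive rules, under which a subject who switches without IRRC-confirmed progression has the event dated after the switch.

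What stands in full is that the size is assumed and that a reader can see progression on the IS from PFS and DOR.

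**Conclusion.** The point holds for TTF read as a measure of the IS regimen. The direction for the 1-year rate follows from the definitions. The size does not, because the share who switch, the time on CS and the toxicity rate are not in the documents. The range of about 1 to 23 points illustrates those assumptions and does not estimate what this trial will show.

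Three stronger readings are tempting and not supported:
- That every switcher is censored before progression. Only those still on CS at the cutoff are. Those who stopped CS for progression, toxicity or death are events, dated late.
- That the median must rise. It usually does, but it can stay the same or fall slightly through the scan-date steps.
- That the trial's efficacy conclusion is inflated. TTF is a secondary, descriptive Kaplan-Meier summary with no hypothesis test, and ORR, DOR and PFS do not use this rule.

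This should be corrected before TTF is reported for the IS, but it does not threaten the primary analysis.

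**What to change.** This changes the analysis only, not whether subjects may switch. In Protocol 7.2.4 and SAP 3.2.5 and 7.2.5:

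1. Define IS-regimen TTF as time from first dose to the earliest of first progression on the IS (dated at that progression, whether or not the subject switches), discontinuation for toxicity, or death.
2. Use investigator-assessed progression in the investigator version and IRRC-assessed progression in the IRRC version.
3. Where a subject switches to CS without IRRC-confirmed progression, count the switch as failure at the switch date in the IRRC version. As a sensitivity analysis, censor at the last adequate assessment before the switch, as SAP Table 2 does for DOR.
4. Apply the censoring rule for subjects alive and on treatment only to those still on the IS without progression.
5. Report time to permanent ME-401 discontinuation on any schedule as a separately named supportive endpoint, with subjects still on drug censored at the cutoff or last on-treatment date.

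The cost is revised wording and one extra derivation. Progression dates and switch records are already needed for PFS, PFS2 and recapture of response, so no new data are required. TTF will be less favourable and closer to PFS, differing mainly through toxicity stops.
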